13.2. Ethical committee

The Law Decree 17 March 2020 n. 18, in art. 17, indicates the ethics committee of the National Institute for Infectious Diseases Lazzaro Spallanzani (IRCCS) as the only national ethics committee for the evaluation of clinical trials on COVID-19. In this capacity, the committee will express the authorization for this study.

Local ethical committees of participating center will provide local authorization if needed according to Regional legislation.

14. Laboratory methods for immunogenicity assessment

14.1. Serology

Specific IgG against S-protein and N-protein will be tested by using commercial CE-IVD chemiluminescence immunoassays. In particular, the anti-S IgG will recognize specifically the S1 and S2 domains of the SARS-CoV-2 virus S-protein protein (LIAISON®SARS-CoV-2 from DiaSorin®); and the anti-N specific IgG will detect recombinant N-protein from SARS-CoV-2 (Abbott Architect SARS-CoV-2 IgG assay, Abbott Diagnostics).

SARS-CoV-2 neutralizing antibodies will be detected by microneutralization assay under BSL3 conditions at INMI laboratories. Briefly, sera will be heat-inactivated, diluted 1:10 in serum-free medium, and titrated in duplicate in two-fold dilutions. Equal volumes of 100 TCID₅₀/well SARS-CoV-2 (2019-nCoV/Italy-INMI) and serum dilutions will be mixed and incubated at 37°C for 30 minutes. Virus-serum mixtures will be added to sub-confluent Vero E6 cells and incubated at 37 °C and 5% CO₂ for two days. Plates will be then stained with Gram's crystal violet + 5% formaldehyde 40% m/v, washed and read at 595nm. Neutralizing antibody titers will be calculated as the last serum dilution presenting the 50% of virus growth inhibition with respect to the control virus.

GRAd32 nAb titers will be determined at ReiThera laboratories by means of a standard neutralization assay based on infection of HEK293 cells with GRAd32 vectors encoding secreted alkaline phosphatase (SEAP) reporter gene. [46] Briefly, SEAP-expressing GRAd32 pre-incubated with serial dilutions of heat-inactivated serum from trial volunteers, is added to semi-confluent HEK293 cells. SEAP activity in the cell supernatant is measured after 24 hours using a chemiluminescent substrate (CSPD). The neutralisation titre is defined as the reciprocal of sera dilution required to inhibit SEAP expression by 50% compared to the SEAP expression of virus infection alone.

14.2. T cell Immunology

To test the ability of vaccine to induce a T cell response, we will quantify and characterize SARS-CoV-2 specific T cells before and after vaccination by ELISpot and multiparametric flow cytometry. Peripheral Blood Mononuclear Cells (PBMC) will be isolated by density gradient centrifugation, counted and resuspended in culture medium supplemented with 10% heat inactivated FBS.

The first immunogenicity analysis will be performed after 2 weeks from vaccination (T2) using fresh isolated PBMC. Specifically, fresh PBMC isolated from peripheral blood of vaccinated subjects at T2 will be stimulated for 18-24 hours with SARS-CoV-2 peptides mix (designed on the S-protein protein) and the IFN- β production by single cells will be evaluated by ELISpot assay. Results will be expressed as Spot Forming Cells (SFC) per million of PBMC.

Moreover, the kinetic of T cell induction after vaccination will be evaluated on frozen PBMC using different T cell assays (ELISpot assay, intracellular staining/flow cytometry and Tetramer staining) with the aim to deeply characterize the vaccine-induced T cell response overtime. Specifically, the ELISpot assay and the intracellular staining/flow cytometry will be performed after in vitro stimulation with S-protein-specific peptides and allow defining the functionality/polyfunctionality (IFN- γ , TNF- α , IL-17, IL-2, IL-10, CD107a) of antigen specific T cell clones. The results of the intracellular staining will be expressed as frequency of specific T cells able to exert one (single functional), two (double-functional), three (triple-functional) or four (quadruple-functional) different functions. Moreover, the Tetramer staining and flow cytometry will allow an ex vivo deep characterization of S-protein-specific T cells to define their phenotype (activated, exhausted, effector, memory).

15. Ethical issues

15.1. Potential Risks for volunteers

The potential risk to participants is considered as low. The potential risks are those associated with phlebotomy and vaccination. In general, recombinant adenoviral vectors are safe. Similar vaccines encoding different antigens have been given to several thousand volunteers (including children) with a good safety profile.

15.1.1. Phlebotomy

The maximum volume of blood drawn over the study period (approximately 465 mL) should not compromise these otherwise healthy volunteers. There may be minor bruising, local tenderness or pre-syncopal symptoms associated with venopuncture, which will not be documented as AEs if they occur.

15.1.2. Vaccination:

GRAd-COV2 has not been used in humans before and therefore will be initially administered at the lower dose of 5×10^{10} vp before progressing to the higher doses of 1×10^{11} and 2×10^{11} in the arms 2,3 ,5 and 6. Potential expected risks from vaccination include local effects such as pain, redness, warmth, swelling, tenderness or itching. Systemic reactions that could potentially occur following immunization with a recombinant adenovirus vaccine include a flu-like illness with feverishness, fatigue, malaise, arthralgia, myalgia and headache.

As with any vaccine, Guillain-Barré syndrome or immune-mediated reactions that can lead to organ damage may occur, but this should be extremely rare. Serious allergic reactions including anaphylaxis could also occur and for this reason volunteers will be vaccinated in a clinical area where Advanced Life Support trained physicians, equipment and drugs are immediately available for the management of any serious adverse reactions (SAR).

15.1.3. Vaccine induced Disease Enhancement

A potential risk exists that the immunity elicited by an investigational candidate vaccine for COVID-19 may provoke an enhancement of the disease upon infection with SARS-CoV-2. This phenomenon has been described only in animal models when testing vaccines against other coronaviruses, and it was shown to be due to vaccine-induced “suboptimal” immune responses, such as poorly neutralizing antibodies and Th2 skewed immune response promoting inflammatory and allergic immune environment upon pathogen encounter.

The vaccine-mediated disease enhancement has not been observed so far in animal models of SARS-CoV-2 infection or vaccination. In addition, the GRAd-COV2 vaccine has been designed to minimize this risk: first, the choice of a prefusion-stabilized SARS-CoV-2 S-protein protein is meant to maximize the induction of properly neutralizing antibodies, and second, the adenoviral vectored vaccine is a potent inducer of Th1 skewed immune responses that are known to prevent or blunt inflammatory and allergic immune responses.

Nevertheless, as recommended by the International Coalition of Medicines Regulatory Authorities (ICMRA) in a meeting held on March 18 2020 (Global regulatory workshop on COVID-19 vaccine development, <http://www.icmra.info/drupal/news/March2020/summary>), this potential risk has been clearly stated in the ICF.

During the study follow up, as an additional safety measure, extra-visits are foreseen in case any subject develops febrile or respiratory symptoms. If the investigator will consider these symptoms compatible with COVID-19, the subject will be assessed for the presence of SARS-CoV-2 infection in respiratory tract samples. This measure is meant to ensure that potential exposure to SARS-CoV-2 in vaccinated subjects will be properly monitored and scored to assess the occurrence of any vaccine-mediated disease enhancement.

15.2. Known Potential Benefits

Volunteers will not benefit directly from participation in this study. However, it is hoped that the information gained from this study will contribute to the development of a safe and effective SARS-CoV-2 vaccine regime. The only benefits for participants would be information about their general health status.

15.3. Declaration of Helsinki

The Investigators will ensure that this study is conducted according to the principles of the current revision of the Declaration of Helsinki.

15.4. Guidelines for Good Clinical Practice

The Investigators will ensure that this study is conducted in full conformity with the Good Clinical Practice (GCP).

15.5. Approvals

The protocol, ICF, participant information sheet and any proposed advertising material will be submitted to an appropriate Ethics Committee and Italian regulatory authorities (ISS and AIFA).

The Investigator will submit and, where necessary, obtain approval from the above parties for all substantial amendments to the original approved documents.

No substantial amendments to this protocol will be made without consultation with, and agreement of, the Sponsor and Co-sponsor. Any substantial amendments to the trial that appear necessary during the course of the trial must be discussed by the Investigator and Sponsor concurrently. If agreement is reached concerning the need for an amendment, it will be produced in writing by the Principal Investigator and will be made a formal part of the protocol following ethical and regulatory approval.

15.6. Informed consent and participant confidentiality

All participants will sign and date the informed consent form before any study specific procedures are performed. At the screening visit, the participant will be fully informed of all aspects of the trial, the potential risks and the time to be spent for attending follow-up visit and the restriction to personal activities. The following general principles will be emphasized:

- A. Participation in the study is entirely voluntary
- B. Refusal to participate involves no penalty or loss of medical benefits
- C. The participant may withdraw from the study at any time
- D. The participant is free to ask questions at any time to allow him or her to understand the purpose of the study and the procedures involved
- E. The study involves research of an investigational vaccine
- F. The study involves genetic analysis for characterization of HLA type
- G. There is no direct benefit from participating
- H. The volunteer's GP will be contacted to corroborate their medical history
- I. The volunteer's blood samples taken as part of the study will be stored indefinitely and samples may be sent outside of Italy and Europe to laboratories in collaboration with the INMI Lazzaro Spallanzani. These will be anonymized.
- J. The aims of the study and all tests to be carried out will be explained.

The participant will be given the opportunity to ask other questions about the trial, and will then have time to consider whether or not to participate. If they do decide to participate, they will sign and date two copies of the consent form (paper document), one for them to take away and keep, and one to be stored at clinical center.

16. Financing and Insurance

16.1. Financing

The clinical trial is funded by ReiThera SRL and IRCCS INMI Spallanzani. IRCCS INMI Spallanzani owns the property of the IMP lot #RL20-0024.

16.2. Insurance

Indemnity and/or compensation for harm arising specifically from an accidental injury and occurring as a consequence of the research participant's participation in the trial for which ReiThera is the research Sponsor will be covered by a no-fault compensation policy with HDI Global SE – DPT. SPECIAL LINES.

**REVISION HISTORY**

Version No.	Effective Date	Summary of Change(s)
Final 1.0	30 Oct 2020	New document.
Final 2.0	18 Jan 2021	Inclusion of imputation method for immunogenicity result below limit of detection.  Further details on derivation of worst post-baseline laboratory value added for clarity.  Typo corrections.
Final 3.0	27 Jan 2021	Administrative change in SAP language upon change of SOP used for protocol deviations. SOP-GDO-WW-012 changed to SOP-EPD-WW-012.
Final 4.0	21 Jun 2021	Imputation rule of BLQ value in anti-S-Ab concentration is updated to $LLOQ/2 = 1.9$ .  Clarification added on external data from frozen ELISpot samples collected on Week 2.

## LIST OF ABBREVIATIONS

List and define all acronyms and abbreviations used in the document here. Abbreviations should be spelled out in full and the abbreviation indicated in parentheses at first appearance in the text. Abbreviations should appear in alphabetical order.

Abbreviation / Acronym	Definition / Expansion
AE	Adverse event
ATC	Anatomical therapeutic chemical
BLQ	Below the lower limit of quantification
BMI	Body Mass Index
BP	Blood pressure
Bpm	Beats per minute
CRF	Case Report Form
CS	Clinically significant
CTCAE	Common Terminology Criteria for Adverse Events
DB	Clinical database
DBHL	Clinical database hard lock
DBP	Diastolic blood pressure
DNA	Deoxyribonucleic acid
DRM	Data Review Meeting
DRM	Data Review Meeting
DSMB	Data safety monitor board
ECG	Electrocardiogram
eDISH	Evaluation of Drug Induced Serious Hepatotoxicity
FA	Final analysis
HBsAg	Hepatitis B surface antigen
HCV	Hepatitis C virus
HIV	Human immunodeficiency virus
HR	Heart rate
IA	Interim analysis

Abbreviation / Acronym	Definition / Expansion
IAS	Immunogenicity analysis set
ICF	Informed consent form
IFN $\gamma$	Magnitude of interferon gamma
IMP	Investigational Medicinal Product
LSLV	Last subject last visit
MedDRA	Medical Dictionary for Regulatory Activities
NA	Not available
NCI	National Cancer Institute (US)
NCS	Not clinically significant
NK	Not known
PBMC	Peripheral blood mononuclear cell
PT	Preferred term
SAE	Serious adverse event
SAF	Safety Analysis Set
SAP	Statistical Analysis Plan
SAS	Statistical analysis system
SBP	Systolic blood pressure
SD	Standard deviation
SFC	Spot forming cell
SOC	System Organ Class
SOP	Standard operating procedure
TEAE	Treatment-emergent adverse event
TLFs	Tables, listings, and figures
WHO-DD	World Health Organisation - Drug Dictionary

## 1 INTRODUCTION

The analyses described in this SAP are based upon the following study documents:

- Study Protocol, Version 2.0 (September 8, 2020)
- electronic Case Report Form (eCRF), Version 4 (generated on August 4, 2020)
- DSMB Charter, Version 2.0

Per protocol, the collected data will be analyzed and reported in three steps according to stages achieved during the course of the study, ie:

Delivery 1: Interim Analysis 1

A report on safety and immunogenicity at 4 weeks for Adults-Cohort will be developed; this report will include:

- a. an analysis of safety issue in the three adults-arms;
- b. pivotal considerations for authorizing enrollment in the Elderlies-Cohort;
- c. a preliminary analysis of immunogenicity in the three adults-arms aimed at identifying the most convenient dose to be used in the eventual phase 2/3 trial.

Delivery 2: Interim Analysis 2

A report on safety and immunogenicity at 4 weeks for Elderlies-Cohort will be developed; this report will include pivotal considerations on:

- a. an analysis of safety issues in the three elderlies-arms
- b. a preliminary analysis of immunogenicity in the three elderlies-arms aimed at identifying the most convenient doses to be used in the eventual phase 2/3 trial.
- c. comparison of safety and immunogenicity between adults and elderlies (across the cohort comparison) to define the most convenient dose to be used either in general population or special groups at risk.

Delivery 3: Final Analysis

Within one year since LSLV final report will be produced including:

- a. Final analysis on safety and immunogenicity at 24 weeks after vaccination in Adults-Cohort
- b. Final analysis on safety and immunogenicity at 24 weeks after vaccination in Elderlies-Cohort

Analyses described hereafter will cover all these three stages of the study with applicable closures on selected analyses if a stage requires.

## 2 STUDY OBJECTIVES

The aim of the program is to prove first in human safety and immunogenicity of the new vaccine GRAd-COV2 considering both healthy adult population and special groups at risk such as the elderlys. The approach includes a phase 1A/1B dose escalation trial with six sequential arms in two cohorts.

### 2.1 Primary Objective(s)

- Provide preliminary information of vaccine safety and immunogenicity in healthy adults within 4 months since trial approval (Adults-Cohort)
- Confirm vaccine safety and immunogenicity in a special population (such as older adults) within 6 months (Elderlies-Cohort)
- Implement an eventual phase 2/3 trial tailored on current Italian epidemic situation at the beginning of 2021.
- Provide full data about safety and immunogenicity at 6 months after vaccination within one year since the approval of the program.

## 3 INVESTIGATIONAL PLAN

### 3.1 Overall Study Design and Plan

This is a first-in-human, open-label, dose escalation, phase 1A/1B clinical trial to assess the safety and immunogenicity of the candidate GRAd-COV2 vaccine in adult volunteers aged 18-55 years and elderly volunteers aged 65-85 years. The vaccine will be administered intramuscularly once in time.

The aim is to enroll 90 volunteers in two cohorts with three arms each (i.e. 15 volunteers per arm in six arms). Each study arm will assess a unique dose of the candidate GRAd-COV2 in a particular population, either adults or elderlys.

### Adults-Cohort (Phase 1A)

Arm-1 will investigate safety and immunogenicity of a dose of 5xE10 vp in adults.

Arm-2 will investigate safety and immunogenicity of a dose of 1xE11 vp in adults.

Arm-3 will investigate safety and immunogenicity of a dose of 2xE11 vp in adults.

### Elderlies-Cohort (Phase 1B)

Arm-4 will investigate safety and immunogenicity of a dose of 5xE10 vp in elderlies.

Arm-5 will investigate safety and immunogenicity of a dose of 1xE11 vp in elderlies.

Arm-6 will investigate safety and immunogenicity of a dose of 2xE11 vp in elderlies.

vp: Viral particles

To minimize the risk of severe adverse events in frail subjects, enrollment of Elderlies-Cohort will start after that 4-week safety results in Adults-Cohort will be available. Moreover, as it is a first in human trial, we have scheduled volunteers to be enrolled according to a strict frame of authorization rules. In particular, each arm includes two groups (A and B). Group As are made of 3 volunteers each to be enrolled throughout a week. The occurrence of SAE within 48h since the injection will be reported to data safety monitor board (DSMB) and the enrolment suspended until a direct effect of the vaccination is excluded. Group Bs are made of 12 volunteer each to be enrolled over a week. DSMB provide advice on sequential enrollment across groups and arms; this is:

- Enrolment of Arm-1 group B and Arm-2 group A is bound to a favorable 7-day safety profile in Arm-1 group A;
- Enrolment of Arm-2 group B and Arm-3 group-A is bound to a favorable 7-day safety profile in Arm-2 group A;
- Enrolment of Arm-3 group B is bound to favorable 7-day safety profile in Arm-3 group A;
- Enrolment of Arm-4 group A is bound to a favorable 4-week safety profile in the whole Arm- 1;
- Enrolment of Arm-4 group B and Arm-5 group A is bound to a favorable 7-day safety profile in Arm-4 group A;
- Enrolment of Arm-5 group B and Arm-6 group-A is bound to a favorable 7-day safety profile in Arm-5 group A;
- Enrolment of Arm-6 group B is bound to a favorable 7-day safety profile in Arm-5 group A.

## 3.2 Endpoints and Associated Variables

### 3.2.1 Safety Variables

- Adverse event (AE) assessments
- Clinical laboratory tests (hematology and clinical chemistry)
- Vital signs (supine blood pressure and pulse, body temperature, respiratory rate and SpO2)
- 12-lead electrocardiograms (ECG): Interpretation
- Physical examinations
- Concomitant medication assessments
- Subject Diary

### 3.2.2 Immunogenicity Variables

- Antibodies to SARS-CoV-2 S-protein (anti-S-Ab)
- Antibodies to SARS-CoV-2 N-protein(anti-N-Ab)
- SARS-CoV-2 micro-neutralization assay
- Magnitude of interferon gamma (IFN $\gamma$ ) ELISpot response (SFC/10 $^6$  PBMC)
- T-cell response (number of positive spike pools-only applicable for fresh PBMC at week 2)

### 3.2.3 Exploratory Variables

## 4 STATISTICAL METHODS

### 4.1 Data Quality Assurance

All tables, figures and data listings to be included in the report will be independently checked for consistency, integrity and in accordance with standard Parexel procedures.

### 4.2 General Presentation Considerations

The overall outline of the scheduled assessment and other study procedures can be found in the Schedule of Assessment, [Table 5](#). In the following, the data handling conventions should be interpreted within the framework of the Schedule of Assessment.

The date of Enrolment Visit (Time 0) is defined as Day 1. All other study days will be labeled relative to Day 1.

- For observation/event dates on or after Day 1, study day for an observation/event date is derived as:  
Observation/event date – visit Time 0 date + 1 day, which could be Day 1, Day 2, Day 3, etc.
- For observation/event dates prior to Day 1, study day for an event date is derived as:  
Observation/event date – visit Time 0, which could be Day -1, Day -2, etc., referring to 1 day, 2 days, etc., prior to Day 1, respectively.
- Day 0 is not defined.

Baseline is considered as the result of last non-missing evaluation before vaccine administration, unless specified otherwise.

End of Study is defined as the last available post-treatment assessment.

Continuous data will be summarized in terms of the mean, standard deviation (SD), median, minimum, maximum and number of observations, unless otherwise stated.

Count data will be summarized in terms of the median, lower and upper quartile, minimum, maximum and number of observations, unless otherwise stated. Geometric mean titer will be provided also for result in titer.

Categorical data will be summarized in terms of the number of subjects providing data at the relevant time point (n), frequency counts and percentages. Any planned collapsing of categories will be detailed in the SAP text and the data displays.

The minimum and maximum will be reported to the same number of decimal places as the raw data recorded in the database. The mean, median, lower quartile and upper quartile will be reported to one more decimal place than the raw data recorded in the database. The SD will be reported to two more decimal places than the raw data recorded in the database. In general, the maximum number of decimal places reported shall be four for any summary statistic. Confidence intervals will be presented to one more decimal place than the raw data.

Percentages will be presented to one decimal place. Percentages will not be presented for zero counts. Percentages will be calculated using n as the denominator. If sample sizes are small, the data displays will show the percentages, but any textual report will describe frequencies only.

Changes from baseline in categorical data will be summarized using shift tables where appropriate.

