6.4. Inclusion criteria

A subject must meet all of the following criteria to be eligible to participate in this study:

1. Provides written informed consent prior to initiation of any study procedures.
2. Be able to understand and agrees to comply with planned study procedures and be available for all study visits.
3. Agrees to the collection of venous blood per protocol.
4. Confirms to have not donated blood three months before the study
5. Agrees to refrain from blood during the study and until the three months after the end of the study.
6. Body Mass Index 18-29 kg/m², inclusive, at screening.
7. Premenopausal women must agree to use one acceptable primary form of contraception.
8. Premenopausal women must have a negative urine pregnancy test the day of vaccination and are routinely using - and willing to use up to six months from vaccine administration - an effective method of birth control resulting in a low failure rate (i.e., hormonal contraception, condoms in combination with a spermicidal cream, male partner sterilization-vasectomy or total sexual abstinence).
9. Oral temperature ≤37.0 degrees Celsius the day of the administration of the vaccine
10. Pulse no greater than 100 beats per minute.
11. Systolic blood pressure (BP) is 85 to 139 mmHg, inclusive the day of vaccination.
12. Should not show laboratory values outside the normal range which may have clinical significance even in absence of specific signs or symptoms.

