7.6. Enrolment visit (Time 0)

Before vaccination, the eligibility of each participant will be reviewed. Investigator will check pulse, blood pressure, temperature, medical history, physical examination and carry out a blood sampling. Testing for time 0 is reported figure 9.

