#### 4.2.2 Imputation of Missing and Incomplete Dates/Times

Every effort will be made to collect complete dates for all study assessments. The following date imputation rules will be applied for missing or partial dates:

- If month and year available, set start date to latest of (1st of the month, first dose date), if end date is complete and imputed start date > end date, set imputed start date to end date – 1
- If year available: Set start date to latest of (January 1st, first dose date), if end date is complete and imputed start date > end date, set imputed start date to end date – 1
- If start date is completely missing, set to first dose date, if end date is complete and imputed start date > end date, set imputed start date to end date – 1.

Completely missing time information will be imputed as 00:00. Partially missing time information with missing hour (xx:mm) or minute (hh:mm) part will be imputed as 00:mm or hh:00, respectively. Missing part will be shown as NK in the listings (where NK = Not Known).

If time is not collected and date of assessment is the same as the first dose date, then assessment will be assumed to be collected prior to treatment unless schedule of assessments and protocol indicate planned collection is always after dosing.

Any AEs with incomplete start and end dates/times will be treated as follows:

Adverse events with unknown start and/or end times (but where the date is known) will be imputed with a time of 00:00 h for the tabulations but will be shown as NK:NK in the listings (where NK = Not Known).

Adverse events with completely unknown start dates will be considered as treatment-emergent for the tabulations and will be shown as NK in the listings. Partially complete AE dates will not be imputed in the listings and the available day, month and year components will be used to determine if an adverse event is treatment-emergent taking the first dosing date and end of study date as references.

Imputing partial AE and prior/concomitant medication start dates:

- a) If the year is unknown, the date will not be imputed and will be assigned a missing value.
- b) If the month is unknown, then:
  1. If the year matches the first dose date, then impute to the month and day of the first dose date.
  2. Otherwise, assign 'January'.
- c) If the day is unknown, then:
  1. If the month and year match the first dose date, then impute to the day of the first dose date.
  2. Otherwise, assign '01'.

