**Table 4 Vital Signs Severity Grading**

Parameter	Severity Grade		
	Mild	Moderate	Severe
SBP	$139 < x \leq 159$	$159 < x \leq 179$	$x > 179$
DBP	$90 < x \leq 99$	$99 < x \leq 109$	$x > 109$
Pulse rate	$49 < x \leq 55$ or $100 < x \leq 115$	$40 < x \leq 49$ or $115 < x \leq 130$	$x \leq 40$ or $x > 130$
	$93 < x \leq 96$	$91 < x \leq 93$	$x \leq 91$
Body temperature	$35.0 < x \leq 35.9$ or $37.5 < x \leq 38.0$	$38.0 < x \leq 39.0$	$x \leq 35$ or $x > 39.0$

If more than one assessment is performed for a time point, then for summaries the most severe grade will be used.

The following summaries will be provided for each vital sign parameter:

- Results and change from baseline will be summarized descriptively by timepoint and treatment group;
- Number and percentage of subjects will be tabulated by severity grade, visit and overall, for each treatment group;
- Shift from baseline severity grade will be presented by visit and overall, for each treatment group;

By-subject listing of vital signs results with change from baseline and severity grade will be provided by subject, vital sign parameter and timepoint for each treatment group.

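### Systolic pressure only: the SAP baseline is the vaccination-day reading that eligibility caps at 139 mmHg, so change from baseline and grade shifts lean upward even with no vaccine effect

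*SAP*

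**What the plan says.** - **Baseline.** SAP 4.2: "Baseline is considered as the result of last non-missing evaluation before vaccine administration, unless specified otherwise". SAP 4.11.5 (Vital Signs) makes no exception.
- **Entry limit.** Protocol 6.4, criterion 11: "Systolic blood pressure (BP) is 85 to 139 mmHg, inclusive the day of vaccination".
- **When it is measured.** Protocol 7.6 reviews eligibility before vaccination, and at that visit "Investigator will check pulse, blood pressure, temperature, medical history, physical examination and carry out a blood sampling". The reading that admits the subject is thus normally also the last pre-dose reading.
- **Grades.** SAP Table 4 grades systolic pressure mild from just above 139, with no grade for low values. Protocol Table 1 leaves 85 to 140 ungraded, so the exact match between entry ceiling and grade cut belongs to the SAP. The two tables need reconciling.
- **Outputs.** SAP 4.11.5: "Results and change from baseline will be summarized descriptively by timepoint and treatment group". It also asks for a shift table of severity grade against baseline, by visit and overall.
- **Visits.** Both schedules mark blood pressure at screening, at T0 and at seven later visits (D2, W1, W2, W4, W8, W12, W24).
- **Design.** The study is open label and every participant is vaccinated, 15 per arm in six arms.

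**The concern.** A baseline selected for not being high understates the subject's usual pressure on average. Readings at later visits are not selected, so they drift back up. This is regression to the mean, and it needs no vaccine effect. Because the SAP grade starts exactly where eligibility stops, nobody who met the criterion can be graded at baseline. Ordinary visit-to-visit variation then appears in the shift table as new mild or worse systolic elevation, and the overall column collects it across visits. Without a control arm, nothing in the trial shows how much of the shift is artefact. A reader of the within-arm tables could take it for a reaction to the vaccine.

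**Working it through.** **Figures in the plan.** There is none to reproduce. The documents give no systolic mean, SD, between-visit correlation or expected change. All sizes below rest on assumed distributions with no vaccine effect.

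**Formula.** If readings at two visits are bivariate normal with the same mean μ, SD σ and correlation ρ, and the first is kept only when at or below 139, then

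E[later − baseline] = (1 − ρ) × σ × φ(c)/Φ(c), with c = (139 − μ)/σ.

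This is positive whenever ρ is below 1. The formula ignores the lower limit of 85, which matters little here.

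**Worked case.** μ = 132, between-person SD 12, within-person SD 8:
- σ = √(144 + 64) = 14.42; ρ = 144/208 = 0.692; c = 7/14.42 = 0.485
- φ(c) = 0.355; Φ(c) = 0.686
- change = 0.308 × 14.42 × 0.355/0.686 = 2.3 mmHg (simulation: 2.28)

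**Simulation.** 400,000 subjects per setting, between-person SD 12, kept if T0 is 85 to 139, seven later visits. Null mean change from T0 (mmHg):

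| True mean | within SD 6 | within SD 8 | within SD 10 |
|---|---|---|---|
| 120 | 0.39 | 0.73 | 1.13 |
| 128 | 0.96 | 1.68 | 2.57 |
| 132 | 1.34 | 2.28 | 3.40 |
| 136 | 1.77 | 2.95 | 4.38 |

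Share above 139, against 0% at baseline:
- Mean 120: 4-8% at any one visit, 13-28% at one or more of seven.
- Means 128 to 136: 9-26% and 27-65%.

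The seven-visit figures apply to the final analysis. The interim analyses cut at the last subject's Week 4 visit and will include fewer visits.

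**Second set of assumptions.** Total SD and correlation are set directly, with the cap at 139.5 to allow for whole-number readings. For ρ from 0.8 down to 0.5 the null change is:
- mean 118, SD 12: 0.2 to 0.5
- mean 122, SD 13: 0.5 to 1.2
- mean 130, SD 15: 1.3 to 3.3
- mean 135, SD 16: 2.0 to 5.0

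At ρ = 0.6, 24% (122/13) and 61% (135/16) are newly graded at one or more of seven visits. In an arm of 15 that is about 4 (0.24 × 15 = 3.6) and 9 (0.61 × 15 = 9.2) people.

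**Scale against noise.** The standard error of a mean change with n = 15 and ρ = 0.6 is SD × √(2 × 0.4/15): 3.0 mmHg at SD 13 and 3.7 at SD 16, ignoring truncation.

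**Other vital signs.** Criterion 9 is "Oral temperature ≤37.0 degrees Celsius the day of the administration of the vaccine" and criterion 10 is "Pulse no greater than 100 beats per minute". Assuming temperature mean 36.4-36.5 °C, SD 0.35, ρ = 0.4, the null rise is 0.02 to 0.03 °C. Assuming pulse mean 72, SD 10, ρ = 0.6, it is 0.03 bpm. Both are negligible. Diastolic pressure and SpO2 have no entry cap.

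**Screening as reference (ρ = 0.6, mean 135, SD 16).** Null change is 4.0 mmHg from T0, 2.0 from the mean of screening and T0, and 0.0 from screening. If screening pressure was also used to exclude people above 139, the change from screening is 2.9.

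**The case against.** The strongest reply is about weight. The study is descriptive and tests no hypotheses. The change-from-baseline primary endpoint (Protocol 4.2.1 D) covers laboratory measures, not vital signs. At a mean near 120 the mean shift is about 1 mmHg or less against a standard error of about 3. The SAP also tabulates raw values and grades by visit, so the baseline-referenced displays are not the only view. All of this stands and keeps the point modest. It does not remove it: the shift is systematic and recurs in every arm, and the shift table is affected far more than the mean.

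A reader might also infer more than the documents support:

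- **Larger in the elderly as a fact.** No systolic distribution is given for either cohort. With equal distributions the excess is zero.
- **Distorted dose comparison.** All arms in a cohort face the same cap, so the bias cancels between doses in expectation.
- **Worst of repeats as a driver.** SAP 4.11.5 says "If more than one assessment is performed for a time point, then for summaries the most severe grade will be used". This acts on grades, not on mean change, and only if repeats are taken. The schedules mark blood pressure once per visit. T0 is itself a time point, so an asymmetry between baseline and later visits is only one reading.
- **Untimed vaccination-day readings.** SAP 4.2.2 says that for an untimed reading on the dosing date, "then assessment will be assumed to be collected prior to treatment", with an exception where planned collection is always after dosing. Neither schedule lists a vital-sign reading in the observation period. A post-dose reading would not be capped by eligibility, so using it as baseline would not add to this bias.

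**Conclusion.** The point holds for systolic pressure. The capped T0 reading is the baseline, the SAP grade begins at the cap, and both mean change and the shift table lean upward under no effect. That direction follows from the documents for any between-visit correlation below 1. The size does not: the ranges above depend entirely on assumed means, SDs and correlations. On those assumptions the mean effect is small near 120 mmHg and a few mmHg nearer the cap. The overall shift column is where a reader is most likely to be misled. Within-arm change is affected. The adult-versus-elderly contrast is affected only if elderly systolic pressure lies nearer 139 or varies more. The allowance for well-controlled patients on sartans or ACE inhibitors makes values near the cap plausible, but it applies to both cohorts and does not settle the matter.

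**What to change.** In SAP 4.11.5, for systolic pressure only:

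1. Keep the T0 baseline. Beside it, add change from the screening reading and shift from the screening grade.
2. Show the screening grade distribution next to each post-vaccination visit.
3. Footnote the T0-based displays: T0 systolic pressure is truncated by criterion 11, so upward shifts, above all in the overall column, are expected without any vaccine effect.

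Do not define the baseline grade as the worse of screening and T0 for uncapped parameters. For diastolic pressure, assuming mean 82, between-person SD 7 and within-person SD 6, that would grade 29% at baseline against 19% at a single later visit, a false improvement.

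The cost is SAP wording and one extra display, using readings already collected. The limit is that the screening reference corrects the bias only partly, or not at all, if systolic pressure at screening was also used in practice to exclude subjects. The report should state whether it was.
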